Date: 01.01.2020

The Effect of Estradiol Valerate, Lng-IUD, and Micronized Progesterone Treatment On Health Quality of Patients with Heavy Menstrual Bleeding

Women who were admitted and treated for heavy menstrual bleeding were asked to participate in this comparative study. Women were eligible for entry if they had self-described heavy menstrual bleeding, had a regular cycle, had completed their family and were 40–50 years old at initial assessment.

After a thorough physical examination and ultrasonographic evaluation, all women underwent endometrial biopsy before the study by using a Pipelle endometrial suction curette to rule out any organic endometrial pathology. Blood samples were analysed to test for hemoglobin (Hb), hematocrit (Hct), ferritin, serum iron and iron-binding capacity and coagulation tests such as prothrombin time and activated partial thromboplastin time.

The study was approved by the Institutional Review Board and Local Ethics Committee. After they gave written informed consent, patients who fulfilled eligibility criteria were recruited to one of the following 3 groups:

Group 1: Women who were treated with estradiol valerate/dienogest regimen for heavy menstrual bleeding. 28 days of E2V/DNG was administered using a dynamic dosing regimen. (E2V 3 mg on days 1–2, E2V 2 mg/DNG 2 mg on days 3–7, E2V 2 mg/DNG 3 mg on days 8–24, E2V 1 mg on days 25–26 and placebo on days 27–28).

Group 2: Women who were treated with LNG-IUD for heavy menstrual bleeding. LNG-IUD is containing 52 mg levonorgestrel at initial placement and releases 20 microgram levonorgestrel per day. This is approved for 5 years of use by the US FDA for treatment of HMB.

Group 3: Women who were treated with oral Micronized Progesterone 200 mg for heavy menstrual bleeding. Cyclic, luteal-phase administration of progestin remained a widely used but little research treatment strategy for HMB for several decades.

None of the recruited patients were not prescribed oral iron preparations and patients who were symptomatic because of anemia (hb<10 mg/dl) were excluded.

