Baseline characteristics of women are age (years), body mass index, parity, current smoker, days of bleeding, length of cycle (days), number of days of heavy bleeding, number of days of painful bleeding, unable to leave house on heaviest days, number of days housebound, number of nights disturbed, Pictorial Bleeding Assessment Chart (PBAC) score (A monthly score of 100 or more on this chart is significantly associated with heavy menstrual bleeding of more than 80 ml per cycle, as measured by the alkaline haematin method), endometrial thickness at time of treatment (mm), uterine size (length x width).

The Exclusion criteria are

1. ultrasound abnormalities (submucosal fibroids, intramural fibroids greater than 3 cm in diameter, large subserosal fibroids, endometrial polyps);
2. laboratory abnormalities (follicle stimulating hormone level higher than 40 iu/l, adverse endometrial histology)
3. hysteroscopic abnormalities (submucosal fibroids, endometrial polyps),
4. incidental adnexal abnormality on ultrasound,
5. severe intermenstrual bleeding, severe dysmenorrhoea, severe premenstrual pain, chronic pelvic pain,
6. medical contraindications to either study treatment,
7. previous endometrial ablation or resection,
8. uninvestigated postcoital bleeding
9. untreated abnormal cervical cytology.

10. pregnancy; lactation; occurrence of <3 menstrual cycles following childbirth, abortion or lactation;
11. current use of an intrauterine device; hypersensitivity to any of the study drug ingredients and known or suspected malignant or premalignant disease.
12. systemic diseases like hypertension, diabetes, thyroid diseases or coronary artery diseases; and history of previous medication for menorrhagia
13. using anticoagulant drugs

Women who were recruited the study will be assessed at 1,3 and 6 months with Hot Flush Rating Scale (HFRS), Menopause Rating Scale (MRS), menorrhagia multi-attribute scale (MM-AS), pictorial bleeding assessment chart and blood sample analysis.

The primary outcomes assessed

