1. Hot flush rating scale: Measures included the HFRS, a self-report measure of frequency and problem rating of Hot Flushes/Night Sweats over the past week. Problem rating is calculated as the mean of the scores on three ten-point scales assessing the extent to which Hot Flushes/Night Sweats are problematic, distressing and causing interference in daily life. Scores for the problem rating range between 1 and 10, with higher scores indicating more problematic Hot Flushes/Night Sweats. The HFRS has been found to have reasonable test–retest reliability and good concurrent validity.
2. Menopause rating scale: The Menopause Rating Scale (MRS) is a questionnaire that assesses the presence and intensity of 11 menopausal symptoms. These are grouped into three subscales: the somatic subscale: assessing hot flushes/sweating, heart discomfort, sleeping problems, and muscle and joint discomfort (items 1–3 and 4 respectively); the psychological subscale: assessing depressive mood, irritability, anxiety, and physical and mental exhaustion (items 4–7 respectively); and the urogenital subscale: assessing sexual problems, bladder problems and vaginal dryness (items 8– 10, respectively). Each of the 11 items can be rated by the participant

from 0 (not present) to 4 (1 ¼ mild, 2 ¼ moderate, 3 ¼ severe and 4 ¼ very severe). The scores obtained for each individual item are summed to provide the corresponding total subscale score. The sum of subscales scores provide the total MRS score. Higher scores are indicative of more severe symptoms. Indeed values above 8 (somatic), 6 (psychological), 3 (urogenital) and 16 (total MRS) were defined as severe.

The secondary outcomes assessed

1. Quality of life as measured by menorrhagia multi-attribute scale: which is designed to measure the effect of menorrhagia on six domains of daily life (practical difficulties, social life, psychological health, physical health, work and daily routine, and family life and relationships). Summary scores, which range from 0 (severely affected) to 100 (not affected)
2. Menstruation, by pictorial bleeding assessment chart
3. Haemoglobin levels were also measured at pre-treatment, 1, 3 and 6 months.
4. Adverse event (Breast pain, Headache, Acne, Alopecia, Migraine, Increase in body weight...)

Statistical analysis

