Data analysis was performed by using SPSS (IBM SPSS Statistics for Windows, Version 20.0. Armonk, NY: IBM Corp.). A one-sample Kolmogorov–Smirnov test was performed to analyze the distribution of clinical variables. The frequency and percentage of the categorical variables and the mean, standard deviation of the continuous and ordinal variables were presented. The study groups were compared using One-way analysis of variance (ANOVA) test for parametric variables and the Kruskal Wallis H test for the non-parametric variables. Wilcoxon signed rank test was used for the comparison of the BAI and FSFI scores at the first visit and second visits. For all calculations, a p-value of <0.05 was considered statistically significant.

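### No random allocation is stated, the three treatment groups are compared without adjustment, and no pre-treatment HFRS, MRS or MM-AS is stated, so differences present before treatment can be read as treatment effects

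*Combined protocol and SAP*

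**What the plan says.** - **Allocation.** The opening section calls the work a comparative study and says "patients who fulfilled eligibility criteria were recruited to one of the following 3 groups". Each group is then described by what its members received, for example "Women who were treated with LNG-IUD for heavy menstrual bleeding". No randomisation, sequence, concealment or other assignment rule appears anywhere.
- **Baseline data.** The list begins "Baseline characteristics of women are age (years), body mass index, parity, current smoker, days of bleeding" and goes on to cycle and bleeding variables, the pictorial bleeding chart (PBAC) score, endometrial thickness and uterine size. HFRS, MRS and MM-AS are not in it.
- **Assessments.** Women "will be assessed at 1,3 and 6 months with Hot Flush Rating Scale (HFRS), Menopause Rating Scale (MRS"), followed by MM-AS, PBAC and blood samples.
- **Haemoglobin.** The secondary outcomes give it an explicit baseline: "Haemoglobin levels were also measured at pre-treatment, 1, 3 and 6 months".
- **Analysis.** Under Statistical analysis the between-group tests are given as "The study groups were compared using One-way analysis of variance (ANOVA) test for parametric variables and the Kruskal Wallis H test" for non-parametric variables. No covariate, change score, stratification or propensity method is named. The only within-patient test reads "Wilcoxon signed rank test was used for the comparison of the BAI and FSFI scores at the first visit and second visits"; neither BAI nor FSFI is an outcome of this study.

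**The concern.** A comparison of raw scores across treatment groups supports a causal reading only if the groups would have had the same score distribution without treatment. Random allocation provides that, but the plan does not claim it. Without it, the usual safeguard is adjustment for the pre-treatment value of the outcome and for other prognostic factors. The plan names no such adjustment, and for both primary outcomes it does not say that a pre-treatment value will exist.

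A group with more vasomotor or menopausal symptoms at entry could therefore appear to have been made worse by its treatment, or the reverse. Entry restriction (age 40 to 50, a regular cycle, exclusion for "follicle stimulating hormone level higher than 40 iu/l") narrows such differences but does not remove them. This is bias, so recruiting more women makes a false conclusion more likely, not less.

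**Working it through.** **What the text supports, outcome by outcome**

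| Outcome | Pre-treatment value stated? | Used in a named analysis? |
|---|---|---|
| HFRS (primary) | No | No |
| MRS (primary) | No | No |
| MM-AS | No | No |
| PBAC | Yes, baseline list | Not for adjustment |
| Haemoglobin | Yes, secondary outcomes | Not for adjustment |

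Age, BMI, parity and smoking are also collected. ANOVA may be meant to compare them between groups, but that describes imbalance and does not correct for it.

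**Illustration of size**

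The plan has no sample size, SD or effect size, so there is no figure of its own to reproduce. The only input from the plan is alpha = 0.05. Assumed inputs: three equal groups of n = 30, 50 or 100; no treatment effect; one group shifted at baseline by d = 0.3 or 0.5 SD; baseline-to-follow-up correlation ρ = 0.5 or 0.7.

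The shift δ remaining at follow-up depends on how the imbalance acts:

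- Case A, only through the baseline score: δ = ρd.
- Case B, persisting in full: δ = d.
- Case C, groups balanced: d = 0.

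For unadjusted ANOVA the rejection rate comes from the noncentral F distribution with 2 and 3n − 3 degrees of freedom. With group means 0, 0 and δ, the noncentrality is λ = n·δ²·2/3. Example, case A, n = 50, d = 0.5, ρ = 0.7: δ = 0.35, λ = 50 × 0.1225 × 2/3 = 4.08, rejection 41.6%. The same setting in case B: δ = 0.5, λ = 50 × 0.25 × 2/3 = 8.33, rejection 72.7%.

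ANCOVA on the baseline score was simulated (20,000 trials per setting; 10,000 at n = 100). Ranges run over d and ρ.

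| n per group | A: ANOVA | A: ANCOVA | B: ANOVA | B: ANCOVA |
|---|---|---|---|---|
| 30 | 8–26% | about 5% | 20–49% | 8–18% |
| 50 | 11–42% | about 5% | 32–73% | 9–27% |
| 100 | 18–72% | about 5% | 58–96% | 14–52% |

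Kruskal-Wallis behaves alike at the extreme settings: 8.7% to 68.1% in A and 17.7% to 95.4% in B.

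In case B the bias left after adjustment is d(1 − ρ), from 0.3 × 0.3 = 0.09 SD to 0.5 × 0.5 = 0.25 SD, against 0.3 to 0.5 SD unadjusted. At n = 50, d = 0.5, ρ = 0.7, ANCOVA rejects in about 17% of trials against 73% without adjustment.

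In case C both tests reject in about 5%. Adjustment then removes a share ρ² of the residual variance: 0.5² = 25% to 0.7² = 49%.

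**The case against.** **The baseline gap rests on silence in lists that are incomplete.** Haemoglobin is missing from the baseline list, yet it is measured before treatment. PBAC is in the 1, 3 and 6 month sentence and also has a baseline value. That sentence may be only a follow-up schedule. This stands as a caution: the text shows that no pre-treatment HFRS, MRS or MM-AS is stated, not that none is taken. If they are taken, recording them is only a wording change, but no named analysis uses them.

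**The bias is conditional.** The documents do not say that allocation was non-random, and under random allocation the unadjusted tests keep their 5% level. That is right. But the plan does not let a reader tell which case applies.

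**The analysis section does not say which variables, visits or scale the tests apply to.** Change scores are not excluded. Nor are they stated, and for HFRS, MRS and MM-AS they would need a baseline that is not stated either.

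**The illustration uses no input from the plan beyond alpha.** True. It shows direction and possible size, and it ignores that these scales are bounded and may sit near their floor in women with regular cycles. The concern does not depend on it.

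**ANCOVA is not the only remedy.** In case B a change score is unbiased and keeps about 5%. In case A it is biased by d(1 − ρ) in the opposite direction and rejects in 7% to 43%, while ANCOVA keeps about 5%. Neither dominates when allocation is unknown. This stands, and it justifies adding a change-score sensitivity analysis.

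**Conclusion.** The concern holds and needs correcting before results are interpreted. No allocation rule is given, the only between-group tests are unadjusted, and neither primary outcome has a stated pre-treatment value. If allocation was not random, the planned comparison cannot separate treatment effects from earlier differences. Under the assumed imbalances (0.3 to 0.5 SD, correlation 0.5 to 0.7, 30 to 100 women per group), a nominal 5% test rejects in 8% to 96% of trials with no treatment effect. If allocation was random, the cost is precision only: 25% to 49% of residual variance left in.

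The reading of the text is certain. The presence and size of bias in this study are not, because they depend on an allocation method that the plan does not disclose.

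**What to change.** 1. Administer HFRS, MRS and MM-AS at the existing pre-treatment assessment as well as at 1, 3 and 6 months; if this is already intended, say so.
2. Make the main outcome comparison an ANCOVA, or a repeated-measures mixed model over the three visits. Adjust for the pre-treatment value of the outcome and for prespecified covariates already collected, such as age, BMI, smoking and baseline PBAC. For clearly non-normal scales use rank ANCOVA or ordinal regression with the same covariates. PBAC and haemoglobin can be adjusted with values already planned.
3. Report adjusted pairwise differences with 95% confidence intervals. Keep the unadjusted tests as supportive and add a change-score analysis as a sensitivity check.
4. State how women are allocated. If not at random, describe results as associations and name residual confounding as a limitation.

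**Cost.** Three self-report questionnaires per woman at an assessment that already includes examination, ultrasound, biopsy and blood samples, plus analysis-plan wording. The example covariates use about 5 degrees of freedom: at an assumed 30 per group, error df falls from 90 − 3 = 87 to 82. No extra patients are needed.

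**Limits.** Adjustment does not remove all confounding, as case B shows. The text mixes past and future tense. If some women have already started treatment without completing the scales, those baseline scores cannot be recovered, and adjustment for these women is limited to covariates already collected.

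### Classical one-way ANOVA may not hold its 5% level if group sizes and SDs both differ; prespecifying Welch's ANOVA is a cheap safeguard

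*Combined protocol and SAP*

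**What the plan says.** All references are to the combined protocol and SAP.

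- **Between-group test.** Under Statistical analysis: "The study groups were compared using One-way analysis of variance (ANOVA) test for parametric variables", followed by "the Kruskal Wallis H test for the non-parametric variables". There are therefore two routes.
- **Screen.** "A one-sample Kolmogorov–Smirnov test was performed to analyze the distribution of clinical variables". The plan does not say outright that this test decides the route, but no other rule is given.
- **Level.** "a p-value of <0.05 was considered statistically significant".
- **Group formation.** After consent, "patients who fulfilled eligibility criteria were recruited to one of the following 3 groups". No total, group size, allocation ratio or randomisation is given.
- **Scales.** For the hot flush rating scale (HFRS, primary): "Scores for the problem rating range between 1 and 10". The menopause rating scale (MRS, primary) has 11 items scored 0 to 4, so its total runs from 0 to 11 × 4 = 44.
- **Spread.** "the mean, standard deviation of the continuous and ordinal variables were presented". SDs will be reported, but none is assumed in advance. No test of equal variances and no unequal-variance method is named.

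**The concern.** The one-way F test divides the variation between group means by a pooled within-group variance. Pooling is right if the groups share one variance. If they do not, the pooled figure is weighted toward the spread of the largest group. When the smallest group is the most variable, the denominator is too small and the test rejects too often. When the largest group is the most variable, the test rejects too seldom.

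The plan does not secure either of the conditions that would make this harmless, equal sizes or equal variances. At stake is whether p<0.05 in the between-group comparisons, including those on the primary scales, means what it says. The direction of any error cannot be known in advance.

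**Working it through.** The plan states no sample size, SD or effect size, so it has no figure of its own to reproduce. The inputs taken from it are 3 groups, a level of 0.05 and the HFRS range of 1 to 10. **All sizes and SDs below are assumptions.** SDs are listed in the same order as sizes, so the third group always has the largest.

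**1. Direction, by expectation.** With equal means, N = Σnᵢ and k = 3:

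E(MS between) = Σ(1 − nᵢ/N)σᵢ² / (k − 1); E(MS within) = Σ(nᵢ − 1)σᵢ² / (N − k). The F test needs a ratio of 1.

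- 60/40/20, SD 1:1:2. Between: (0.500 + 0.667 + 0.833 × 4)/2 = 2.25. Within: (59 + 39 + 19 × 4)/117 = 1.49. Ratio 1.51, so too many rejections.
- 20/40/60, SD 1:1:2. Between: (0.833 + 0.667 + 0.500 × 4)/2 = 1.75. Within: (19 + 39 + 59 × 4)/117 = 2.51. Ratio 0.70, so too few.
- 50/50/50, SD 1:1:2. Between: 0.667 × 6/2 = 2. Within: 49 × 6/147 = 2. Ratio 1.

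**2. Welch's statistic.** With wᵢ = nᵢ/sᵢ², W = Σwᵢ, weighted mean m = Σwᵢx̄ᵢ/W and Λ = Σ(1 − wᵢ/W)²/(nᵢ − 1):

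F = [Σwᵢ(x̄ᵢ − m)²/(k − 1)] / [1 + 2(k − 2)Λ/(k² − 1)], on k − 1 and (k² − 1)/(3Λ) degrees of freedom.

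The code for both tests matched statsmodels (Welch) and scipy (classical) p-values on a test data set.

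**3. Type I error, normal data, equal means.** 40,000 replicates per scenario; Monte Carlo standard error near 5% is √(0.05 × 0.95/40,000) = 0.11 points. Entries are percentages. The first three numeric columns are the classical F test; the last is Welch's range over the same three SD patterns.

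| Sizes | SD 1:1.25:1.5 | SD 1:1.5:2 | SD 1:1:2 | Welch |
|---|---|---|---|---|
| 30/30/30 | 5.1 | 5.5 | 6.0 | 4.7–4.9 |
| 50/50/50 | 5.1 | 5.6 | 5.9 | 4.9–5.1 |
| 40/30/20 | 7.3 | 9.3 | 10.7 | 4.9–5.0 |
| 60/40/20 | 8.9 | 12.0 | 14.1 | 5.0 |
| 75/30/15 | 11.2 | 16.5 | 17.0 | 5.0–5.1 |
| 20/30/40 | 3.5 | 3.2 | 3.1 | 4.9–5.1 |
| 20/40/60 | 3.0 | 2.3 | 2.0 | 4.9–5.0 |
| 15/30/75 | 2.1 | 1.5 | 0.6 | 5.1–5.3 |

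With equal SDs the classical test gave 4.9% to 5.1% at every split.

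**4. Skewed, floor-bounded scores.** Scaled beta on 1 to 10 with mean 3 in every group (HFRS-like), SDs 1, 1.5 and 2:

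- 30/30/30: classical 5.9%, Welch 5.7%.
- 60/40/20: classical 11.7%, Welch 6.2%.
- 20/40/60: classical 2.4%, Welch 5.1%.

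Welch's highest value was 6.3% (60/40/20, SDs 1.2, 1.6 and 2.0; classical 10.1%). With all SDs equal to 2 at 60/40/20, Welch gave 5.9% and the classical test 5.1%.

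**5. Power cost when SDs are equal** (normal data, means 0, 0 and 0.6 SD), classical to Welch:

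- 30/30/30: 65.5% to 64.6%, a loss of 0.9 points.
- 50/50/50: 87.8% to 87.4%, 0.4 points.
- 20/40/60: 83.4% to 82.3%, 1.1 points.
- 60/40/20: 57.3% to 55.6%, 1.7 points.

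**6. Pairwise comparisons, large samples, equal sizes, SD 1:1:2.** The pooled variance is (1 + 1 + 4)/3 = 2, so a difference between two means is given variance 2 + 2 = 4 in units of 1/n. For groups 1 and 2 the truth is 1 + 1 = 2; the effective cut-off is 1.96 × √(4/2) = 2.77 and the error about 0.6%. For groups 1 and 3 the truth is 1 + 4 = 5; the cut-off is 1.96 × √(4/5) = 1.75 and the error about 8%. Equal sizes therefore protect the overall test but not pairwise tests that use the pooled variance.

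**The case against.** **Nothing in the documents shows unequal sizes or unequal SDs.** This stands. Sizes that are not fixed need not be unequal, and a large error needs both conditions at once. With equal sizes and SD ratios up to 2:1, the overall test is at 5.1% to 6.0%.

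**Floor effects do not by themselves create the problem.** A reader might infer that the treatments will compress the spread of floor-bounded scores, so that the 5% level is lost. The documents do not support this. They give no SDs and do not say that any treatment changes the spread. If one group is pressed toward the floor because it improves most, the means differ, and rejecting equality is not a type I error. If the treatments act identically on the whole distribution, the variances are equal. What remains is narrower: different regimens, with no stated randomisation, can have similar means and different spreads.

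**The bleeding score.** A reader might count the bleeding chart among the floor-bounded scales. The outcome list gives only "Menstruation, by pictorial bleeding assessment chart", and the baseline paragraph gives a threshold of 100; no lower bound is stated. The point does not rely on one.

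**Skewed scores may never reach ANOVA.** The Kruskal–Wallis route is real, but it protects only in part. For three assumed beta-shaped scores, the uncorrected Kolmogorov–Smirnov test rejected normality in 1% to 8% of samples at n = 30, and in 20% to 89% at n = 90. Kruskal–Wallis is also not a test of equal means. With equal means and SDs of 1, 1.5 and 2 in the beta scenarios, it rejected in 15% to 23% of trials.

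**Welch is not exact on skewed data.** This stands too, as step 4 of the working shows.

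**Conclusion.** The point holds in conditional form. The plan names a test that assumes equal variances. It neither checks nor allows for unequal ones, and it does not fix group sizes. If sizes and SDs both differ, the F test may run well above or below 5%: about 14% at 60/40/20 and about 2% at 20/40/60 with a 2:1 SD ratio, and 0.6% to 17.0% over the whole assumed grid. Milder departures matter less (7.3% at 40/30/20 with SD 1:1.25:1.5). With equal SDs and normal data the test is exact at any split.

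These figures rest on assumed sizes, SDs and distributions, and they concern equality of means. They do not show that this trial's error rate is wrong. Classical ANOVA is a conventional choice, and the change is a cheap improvement. A reader might also infer a need for robust standard errors in regression, but the plan contains no regression analysis to which that would apply.

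**What to change.** In the Statistical analysis section, for the variables the plan sends to one-way ANOVA:

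- Name Welch's ANOVA as the test, to be used in all cases and not only after a preliminary test of variances.
- For any pairwise comparison of groups, give Games–Howell (unequal-variance) intervals. The plan names no pairwise method at present.

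The cost is a sentence or so in the plan and a choice of options in the SPSS one-way procedure. If variances prove equal, the loss is about 0.4 to 1.7 points of power in the scenarios examined. For strongly skewed scores with unequal sizes, the level may still reach about 6.3%. The change does not affect variables sent to Kruskal–Wallis.

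### The only between-group tests take one value per woman, so loss to follow-up that is related to outcome and differs between groups could bias the 3- and 6-month comparisons

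*Combined protocol and SAP*

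**What the plan says.** The follow-up sentence after the exclusion criteria sets three assessments: "Women who were recruited the study will be assessed at 1,3 and 6 months with Hot Flush Rating Scale (HFRS), Menopause Rating Scale (MRS" and it goes on to name the MM-AS, the bleeding chart and blood tests. HFRS and MRS are the primary outcomes. Haemoglobin also has a pre-treatment value, and PBAC is among the baseline characteristics. No baseline HFRS, MRS or MM-AS is stated.

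For group comparisons, the Statistical analysis section says only: "The study groups were compared using One-way analysis of variance (ANOVA) test for parametric variables and the Kruskal Wallis H test", the latter for non-parametric variables. The one other test is paired: "Wilcoxon signed rank test was used for the comparison of the BAI and FSFI scores at the first visit and second visits". It compares visits and not groups, and neither score is a listed outcome. The threshold is common to everything: "For all calculations, a p-value of <0.05 was considered statistically significant".

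The documents contain no repeated-measures model, baseline adjustment, missing-data rule, analysis set, expected loss or sample size. They do not say at which visit the group tests are run, or on which women.

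**The concern.** A one-way ANOVA or Kruskal-Wallis test needs one number per woman. Run on the month-6 MRS, it drops a woman who gave scores at months 1 and 3 but not at month 6, and makes no use of the scores she gave. If women doing badly leave one group more readily than the others, the women who remain in that group look better at 6 months with no treatment effect at all.

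Unequal loss is plausible here because the treatments differ in form (two oral regimens and an intrauterine device) and the outcomes are the symptoms and bleeding that might prompt a woman to leave. Both primary outcomes are exposed. The earlier scores that could correct part of the problem are already scheduled, but the named tests cannot use them.

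**Working it through.** **Inputs.** From the documents: three groups, visits at 1, 3 and 6 months, threshold 0.05, one-way ANOVA or Kruskal-Wallis. Not in the documents, so assumed: 30, 50 or 100 women per group, SD 1, no true difference, equal correlation ρ between visits, and every loss rate and mechanism below. The plan has no figure of its own to reproduce.

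**Step 1: when bias arises.** Suppose loss depends on the month-1 score Y1 and scores are jointly normal. Among women seen at month 6, the mean score is shifted by ρ × m, where m is the shift in mean Y1 among the retained women. With no treatment effect, the bias between groups A and B is therefore

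bias = ρ × (m_A − m_B).

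If rate and mechanism are the same in both groups, m_A = m_B and the bias is zero. If loss is unrelated to outcome, m = 0 in both and the bias is again zero, even with unequal rates. Bias needs both conditions: loss related to outcome, and a difference between groups.

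**Step 2: size of the bias in one example.** Take 25% loss in A, logistic in Y1 with a log-odds slope of 1.5 per SD, and 10% random loss elsewhere. Retained women in A are then about 0.27 SD better at month 1, so lost women are 0.27 × 0.75 / 0.25 = 0.81 SD worse than the group mean.

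- ρ = 0.5: 0.5 × 0.27 = 0.135 SD
- ρ = 0.7: 0.7 × 0.27 = 0.189 SD

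Simulation gives 0.13-0.15 and 0.19-0.20 SD.

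**Step 3: false-positive rate of the month-6 ANOVA.** There were 3000 simulated trials per setting. The Monte Carlo error at 5% is √(0.05 × 0.95 / 3000) ≈ 0.4 points.

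| Assumed loss by month 6 | ρ | n = 30 / 50 / 100 per group |
|---|---|---|
| None | 0.6 | 4.3 / 5.5 / 5.3% |
| 20% in every group, same dependence on month 1 | 0.6 | 5.1 / 4.9 / 5.1% |
| 20% in every group, same dependence on unseen month 6 | 0.6 | 5.0 / 5.3 / 5.2% |
| 10/10/30%, unrelated to outcome | 0.6 | 4.5 / 4.6 / 5.6% |
| 10/10/30%, month 1, slope 1 in all groups | 0.6 | 6.2 / 6.8 / 8.7% |
| 20/20/20%, month 1, slopes +1, 0, −1 | 0.6 | 7.6 / 11.3 / 19.9% |
| 25/10/10%, slope 0.5 in the first group only | 0.5 | 5.1 / 4.6 / 6.5% |
| same | 0.7 | 5.6 / 6.2 / 7.6% |
| 25/10/10%, slope 1.5 in the first group only | 0.5 | 7.3 / 8.5 / 13.4% |
| same | 0.7 | 9.4 / 12.8 / 22.9% |
| 25/10/10%, slope 1.5 in all groups | 0.5 | 6.0 / 5.2 / 7.3% |
| same | 0.7 | 6.1 / 8.0 / 9.3% |

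Kruskal-Wallis was within about 4 points of ANOVA in every setting with ρ = 0.6 (within 1 point in those shown for loss that is absent, equal or unrelated to outcome), so choosing the rank test does not remove the problem.

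**Step 4: does using earlier scores help?** With ρ = 0.6, adjusting month 6 for the baseline and month-1 values (a simple stand-in for a repeated-measures model) gives 4.3-5.8% in every setting where loss depends on the month-1 score. A mixed model under 25% month-1-dependent loss in one group and 10% random loss in the others (600 trials per setting, so about 0.9 points of error) has bias of at most 0.008 SD and 4.3-5.7% false positives. When loss depends on the unseen month-6 score, differently by group, adjustment leaves about 6-31%, against 6-53% for plain ANOVA.

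**The case against.** A reader might infer that any outcome-related loss invalidates these tests. It does not: rows two and three of the table stay at 5%. A reader might also infer that this trial will have unequal loss, or that 7-23% is its expected error rate. The documents support neither. They give no loss figure and do not mention early stopping or device removal. Stopping treatment is also not the same as missing a visit, and nothing in the plan says that assessments end when treatment does. The upper figures need a steep mechanism (a slope of 1.5 is an odds ratio of e^1.5 ≈ 4.5 per SD) confined to one group. With a slope of 0.5, or the same steep slope in all groups, inflation is small at 30 to 50 women per group.

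Nor does the text say that the tests are run at each visit on the observed women only. That is the natural reading, but carrying values forward is not excluded. Finally, a remedy tested where loss depends only on observed scores is tested on favourable ground, as the last result in step 4 shows.

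All of this stands, and it limits the point to a conditional one. It does not answer the point. The plan names no method that uses a woman's earlier scores and no rule for a missing one; reading in carry-forward would add to the text. A better method is available on data already being collected.

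**Conclusion.** The point holds as a conditional risk. The named tests use one value per woman across a three-visit follow-up, and no missing-data rule accompanies them. If loss by 3 or 6 months is related to outcome and also differs between groups in rate or mechanism, the comparison is biased and the false-positive rate exceeds 5%. If loss is the same across groups, or unrelated to outcome, the rate stays near 5%. The actual size cannot be known from the documents. The range of about 5-8% to about 7-23% rests wholly on the assumed 25/10/10% loss, month-1 dependence with slopes of 0.5 to 1.5 in one group, correlations of 0.5 to 0.7, and 30 to 100 women per group. The change is recommended as a cheap improvement; the documents do not show that the trial's result is or will be biased.

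**What to change.** - Analyse each continuous outcome with one likelihood-based linear mixed model for repeated measures on all post-baseline visits: group, visit, group-by-visit and within-woman correlation. Take the 6-month group contrast from it.
- Include the baseline value as a covariate where it is collected, for example PBAC and haemoglobin.
- Report the number lost and the reasons, by group and visit.
- Keep the per-visit ANOVA or Kruskal-Wallis as a sensitivity analysis.
- Add a sensitivity analysis for loss that depends on unseen scores, for example a delta-adjusted one in which missing values are made progressively worse in one group until the conclusion changes.

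The cost is some analysis wording and modest programming in standard software, with no extra visits or measurements. There are limits. The main model assumes that loss depends on observed data, and a woman with no post-baseline value contributes nothing to it. Skewed scores such as PBAC may need transformation. The plan does not describe random allocation (it says only "patients who fulfilled eligibility criteria were recruited to one of the following 3 groups"), and this change does not remove confounding from that source.
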